COMIRB Protocol

Colorado Multiple Institutional Review Board

[name] [contact] [contact]

Protocol #: 19-1362

Project Title: Safety and efficacy of tofacitinib for immune skin conditions in Down syndrome

Principal Investigator: [name]

Co-PIs: [name]; [name]

Document: COMIRB Protocol

Version Date: 04.26.2024

I. Hypotheses and Specific Aims:

The project described here is a phase II, proof-of-concept, open-label trial that will evaluate the safety and efficacy of a 16-week treatment with Tofacitinib in people with Down syndrome (DS) and an autoimmune and/or autoinflammatory skin condition, collectively referred hereto as 'immune skin conditions.' The driving hypothesis for this project is that hyperactivation of interferon (IFN) signaling leads to a myriad of immune-driven diseases and immunological phenotypes in people with Down syndrome, and that pharmacological inhibition of IFN signaling with Tofacitinib could have multidimensional therapeutic benefits in this population.

Our specific aims are:

1. To define the safety profile of JAK inhibition in people with DS,
2. To determine the impact of JAK inhibition on the immune dysregulation caused by trisomy 21,
3. To define the impact of JAK inhibition on immune skin conditions in DS, and
4. To characterize the impact of JAK inhibition on cognition and quality of life in DS.

Accordingly, our hypotheses are:

1. Treatment with Tofacitinib for 16 weeks in people with DS will not result in a higher frequency of serious adverse events definitely related to treatment than reported in the typical population.
2. Treatment with Tofacitinib for 16 weeks in people with DS will result in statistically significant reduction of IFN transcriptional scores.
3. Treatment with Tofacitinib for 16 weeks in people with DS will result in statistically significant reduction of one or more additional markers of immune dysregulation, including a) circulating levels of inflammatory cytokines, b) levels of neurotoxic metabolites in the IFN-inducible kynurene pathway, and c) levels of autoantibodies.
4. Treatment with Tofacitinib for 16 weeks in people with DS will result in statistically significant percentage improvement in one or more measures of skin pathology, including a) Investigator's Global Assessment, b) Dermatology Life Quality Index, and c) disease-specific scoring metrics.

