Figure 5. Trisomy 21 induces the kynurenine pathway. **A.** Volcano plot showing results of a plasma metabolomics experiment on 120 participants, 72 of them with T21. **B.** Overview of tryptophan catabolism pathways. **C.** Quinolinic acid (QA) is significantly elevated in plasma of people with DS. **D.** RNA-seq shows that *IDO1* is overexpressed in white blood cells from people with DS. **E.** Spearman correlation analyses revealed strong association between activation of the kynurenine pathway and circulating levels of cytokines such as TNF α measured in the same plasma

neuroinflammatory phenotype of DS (90-98) may have therapeutic benefits, even in adults. Given the well-documented negative impact of hyperactive IFN signaling on brain function, from excessive synapse pruning by IFN-activated microglia to global impairments in cognitive function upon acute IFN α administration (99-106), **we hypothesize that reducing IFN signaling via JAK inhibition could improve cognition and behavior regulation in DS**. Of note, Tofacitinib was shown to cross the blood-brain barrier in mice (107). Thus, we will assess changes in selected cognition and overall quality of life metrics for individuals with DS upon JAK inhibition.

IV. Research Methods

B. Outcome Measure(s):

Name. Evaluate the safety of Tofacitinib in people with DS.

Type. Primary Endpoint.

Time Frame. Baseline through 16 weeks.

Brief Description. Adverse events (AEs) will be recorded, classified, and closely monitored by study coordinators and doctors. Based on published safety data, we calculate that we should have no more than two serious adverse events (SAE) definitely related to treatment over the course of 16-weeks in order to demonstrate comparable safety to the typical population.

Name. Change in IFN scores in the transcriptome of white blood cells.

Type. Primary Endpoint.

Time Frame. Baseline and 16 weeks.

Brief Description. Using published methods, IFN scores will be calculated using RNA-seq from whole blood RNA. A two-sided, paired Student's t-test will be used to determine the significance of any changes observed.

Name. Change in IGA.

Type. Secondary Endpoint.

Time Frame. Baseline and 16 weeks.

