An adverse event (AE) is any untoward medical occurrence in a participant during participation in the clinical study or with use of the experimental agent being studied. An adverse finding can include a sign, symptom, abnormal assessment (laboratory test value, vital signs, electrocardiogram finding, etc.), or any combination of these. All AEs will be classified using two criteria: 1) severity, and 2) the likelihood that they are attributed to the study intervention. Additionally, regardless of its severity and attribution classifications, an AE may also be considered “serious” (SAE) and/or an “unanticipated problem” (UAP) if it meets certain criteria. These classifications and criteria are explained in depth below. The severity of AEs is based on their impact on the participant. An AE will be termed: 1) Mild: event has minimal impact on the participant, 2) Moderate: the event causes the participant some inconvenience, 3) Severe: event causes a substantial disruption to the participant’s well-being.

AE/SAEs/UAPs will also be categorized according to the likelihood that they are attributed to Tofacitinib, a classification which must be designated by a study doctor. Specifically, AEs will be categorized as: 1) Definitely related: AE is clearly related to the investigational agent, 2) Possibly related: AE may or may not be related to the investigational agent, 3) Not related: AE is clearly not related to the investigational agent.

An AE is considered unexpected if its nature, severity, or frequency is: 1) not listed in the investigator’s brochure, this study protocol, or informed consent form; and 2) not consistent with the expected natural progression of any underlying disease, disorder, or condition the participant has, including their presenting skin condition and DS.

Finally, any AE, regardless of the above classifications, can also be labeled as a serious adverse event (SAE). An SAE is any AE that results in: 1) death, 2) a life-threatening event, 3) inpatient hospitalization or prolongation of existing hospitalization, 4) a persistent or significant disability/incapacity, 5) a congenital anomaly or birth defect, or 6) an important medical event based upon appropriate medical judgment.

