As described above, our study doctors will monitor AEs and assign a likelihood that they are attributable to Tofacitinib treatment. Published safety data for Tofacitinib for treatment of RA in typical people indicates 9.4 serious adverse event (SAEs)/100 patient years (all SAEs, treatment-related or not) (109). Given that our trial aims to enroll 47 participants for 16 weeks of treatment (though we anticipate up to seven participants would be lost to attrition at various times during the treatment course) for a maximum total of 14.5 patient years of treatment, a comparable number of SAEs is 1.36. Accordingly, and with the knowledge that our population may be more prone to AEs in general without any treatment due to other health conditions, we define the success of our primary endpoint associated with this aim as no more than two SAEs *definitely related* to treatment during the 16-week trial.

For the purposes of ongoing safety monitoring during the optional Extension Arm and after the initially planned 14.5 patient years of treatment time, we will transform this endpoint of "no more than two SAEs definitely related to treatment during the 16-week trial" to an allowable *rate* and apply the same criteria for overall stopping rules. Accordingly, 2 allowable SAEs definitely related to Tofacitinib over the course of 14.5 patient years translates to a rate of 13.83 SAEs/100 patient years (see stopping rules #5 and #6).

Research Methods for Specific Aim 2. To determine the impact of JAK inhibition on the immune dysregulation caused by trisomy 21.

Our results demonstrate that individuals with T21 show obvious signs of immune dysregulation and hyperactivation of IFN signaling at the levels of mRNA signatures, cytokine profiles, and plasma metabolites. In this Specific Aim, we will define whether these inflammatory markers can be driven by Tofacitinib toward values observed in typical people. Importantly, we have already defined the directionality and average

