Specific Aim 3. It is possible that some skin conditions will be more sensitive to JAK inhibition than others. For example, in our experience, AD, the most common of the evaluated conditions among those with T21, is more likely to respond rapidly to JAK inhibition than vitiligo. If this proves to be the case during the initial 10-participant phase, we may revise our inclusion criteria for the remainder of the trial to maximize recruitment of individuals that will experience a clinical benefit within 16 weeks of treatment. It is also possible that we will have responders and non-responders even within the same immune skin condition. Although this would dilute our chances of reaching our endpoints, it could be nonetheless very informative to identify differences in IFN scores, cytokines, metabolites or other clinical variables among the two groups, which would inform the design of follow up trials.

Specific Aim 4. It is possible that changes in cognition may not be discerned during the relatively short time course of treatment. Also, it is possible that not all participants will be able to complete all tasks. However, we have taken steps to minimize these risks associated with a short treatment window by selecting measures that are scalable and highly sensitive to change. We have addressed the attrition concern by selecting measures that are developmentally engaging, brief, and easy to administer, thus reducing threats to validity based on participant motivation issues. Furthermore, to address confounding issues observed in previous DS assessment work, each task specifically minimizes motor, expressive language, and receptive language demands, all areas of pronounced challenge in DS. The proposed assessments, therefore, strike a balance between the most advanced approaches to characterizing cognition while maintaining a high degree of feasibility of administration and minimizing phenotype specific threats to validity and reliability. Nevertheless, during the initial 10-participant phase we will explore other instruments driven by new findings related to DS outcome measure validation.

VII. Data Analysis Plan:

Specific Aim 1. To define the safety profile of JAK inhibition in people with Down syndrome.

Primary Endpoint: Evaluate the safety of Tofacitinib in people with Down syndrome.

Endpoint Definition: no more than two serious adverse events (SAE) *definitely* related to treatment during the 16-week study period (see *Data and Safety Monitoring Plan*).

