Method: This number is based on published safety data for Tofacitinib for the treatment of rheumatoid arthritis in the general population, which indicates a rate of 9.4 SAEs per 100 patient years. Given that our trial aims to enroll 47 participants for 16 weeks of treatment (though we anticipate up to seven participants would be lost to attrition at various times during the treatment course) for a maximum total of 14.5 patient years of treatment, a comparable number of SAEs is 1.36.

Specific Aim 2. To determine the impact of JAK inhibition on the immune dysregulation caused by trisomy 21.

The overall goal of our data analysis plan in this Aim is to define which immune processes dysregulated by T21 can be normalized by Tofacitinib treatment, i.e. returned to values observed in typical people. Importantly, data shown in this proposal demonstrate that we have already defined the directionality and average magnitude of the change between people with and without T21. For example, we determined that IFN scores are significantly higher in people with DS (*Figure 3C*) and expect that Tofacitinib will reduce these values. Whereas some of the features dysregulated by T21 may be normalized by Tofacitinib treatment, others may not, and this will provide an important mechanistic insight to understand the molecular underpinnings of immune dysregulation in DS. Accordingly, the endpoints associated with this Specific Aim focus on effects of Tofacitinib (16 weeks of treatment) on four classes of molecular markers of immune dysregulation:

Primary Endpoint: Change in IFN scores in the transcriptome of white blood cells.

Endpoint Definition: Statistically significant reduction in average IFN scores between baseline and 16 weeks as defined by a two-sided, paired Student's t-test.

Method: To determine the impact of Tofacitinib on IFN scores, a two-sided, paired Student's t-test will be used to compare baseline and 16 weeks of treatment for participants with good compliance with the study drug (2 or fewer missed pills) and without a confounding reported adverse event in the 7 days prior to the Visit 7 endpoint. With 40 participants, we have 80% power to detect an effect size of 0.45 with a p-value <0.05, as calculated by G*Power software.

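### The limit of two definitely related SAEs is derived from a rate that counts all SAEs, so meeting it cannot show safety comparable to the typical population

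*Combined protocol and SAP*

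**What the plan says.** - **Section I, hypothesis 1:** treatment "will not result in a higher frequency of serious adverse events definitely related to treatment than reported in the typical population".
- **Section IV, Outcome Measures, first primary endpoint:** the limit of two SAEs definitely related to treatment is set "in order to demonstrate comparable safety to the typical population".
- **Research Methods for Specific Aim 1:** the published data in rheumatoid arthritis "indicates 9.4 serious adverse event (SAEs)/100 patient years (all SAEs, treatment-related or not"). With 47 participants treated for 16 weeks, exposure is at most 14.5 patient-years (PY) and "a comparable number of SAEs is 1.36". Success is then defined as at most two definitely related SAEs. The reason given for the restriction is that "our population may be more prone to AEs in general without any treatment due to other health conditions".
- **Section VII, Data Analysis Plan, Specific Aim 1:** the entry begins "Endpoint Definition: no more than two serious adverse events (SAE" and restricts the count to definitely related events. The Method states: "This number is based on published safety data for Tofacitinib for the treatment of rheumatoid arthritis in the general population". It repeats 9.4 and 1.36, but without the note that the rate covers SAEs of any attribution.
- **Safety and Adverse Event Monitoring:** there are three attribution levels, and the highest is "Definitely related: AE is clearly related to the investigational agent". The reference rates listed there are for SAEs overall or by event type; none is graded by causality. The same section plans study-wide AE incidence rates per 100 PY in the monthly reports. Under Safety and Adverse Event Reporting, the Annual Report checks AE rates against pre-study assumptions.
- **Participant Discontinuation and Trial Stopping, rules 5 and 6:** these use the same limit of two and its conversion to 13.83 per 100 PY.

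**The concern.** The benchmark counts every SAE in the published population. The trial's count is limited to SAEs that a study doctor puts in the top attribution category, so possibly related and unrelated SAEs drop out. Definitely related SAEs are a subset of all SAEs. The difference therefore runs in one direction: the criterion is easier to meet than a like-for-like comparison would be.

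This is one of two primary endpoints. Research Methods for Specific Aim 1 explains that it exists because JAK inhibition may have a different safety profile in Down syndrome (DS). As written, a count of two or fewer could be reported as comparable safety although the two quantities measure different things. Hypothesis 1 has the reverse gap: it names the filtered quantity on both sides, but no filtered reference rate is supplied, so it cannot be tested as stated.

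**Working it through.** **Inputs.** From Research Methods for Specific Aim 1: 9.4 SAEs per 100 PY (all SAEs), 47 participants, 16 weeks, limit of two. From the stopping rules: 13.83 per 100 PY. The share of SAEs rated definitely related is not in the documents and is treated as an assumption.

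**1. The plan's own figures reproduce.**
- Exposure: 47 × 16/52 = 14.46 PY (stated as 14.5).
- Expected SAEs of any attribution: 9.4 × 14.5/100 = 1.363 (stated as 1.36).
- Allowed rate: 2/14.46 × 100 = 13.83. With the rounded 14.5 it is 13.79, a rounding difference only.

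The arithmetic is sound. The question is what the figures are compared with.

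**2. What a matched benchmark would be.** If a share f of the 9.4 were definitely related, the matched expected count would be 1.363 × f, and the allowed rate would be 13.83/(9.4 × f) times the matched rate.

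| Assumed f | Matched expected count | 13.83 as a multiple of the matched rate |
|---|---|---|
| 100% | 1.36 | 1.5 |
| 50% | 0.68 | 2.9 |
| 25% | 0.34 | 5.9 |
| 10% | 0.14 | 14.7 |

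**3. Effect of the filter on the chance of passing.** With a Poisson count of mean μ, P(pass) = P(X ≤ 2) = e^(−μ)(1 + μ + μ²/2). As an illustration, let the trial's true all-SAE rate be three times the benchmark, so 3 × 1.363 = 4.089 SAEs are expected.

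- All SAEs count: μ = 4.089, P(pass) = 22.5%.
- Constant share f rated definite, μ = 4.089 × f: f = 50%, μ = 2.045, 66.5%; f = 25%, μ = 1.022, 91.6%; f = 10%, μ = 0.409, 99.2%.
- Excess caused by the drug, with a share f0 of the background events and a share g of the excess rated definite, μ = 1.363 × f0 + 2.726 × g:

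| f0 | g = 50%: μ, P(pass) | g = 100%: μ, P(pass) |
|---|---|---|
| 10% | 1.499, 80.9% | 2.862, 45.5% |
| 25% | 1.704, 75.6% | 3.067, 40.8% |
| 50% | 2.045, 66.5% | 3.408, 33.8% |

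Across these assumptions P(pass) runs from about 34% to 99%. It exceeds the like-for-like 22.5% in every case.

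**4. A separate matter: precision.** Even if both sides counted all SAEs, the exact Poisson two-sided 95% upper limit for x events is χ²(0.975; 2x + 2)/2 ÷ 14.5 × 100.

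| Events | Upper limit per 100 PY | Multiple of 9.4 |
|---|---|---|
| 0 | 25.4 | 2.7 |
| 1 | 38.4 | 4.1 |
| 2 | 49.8 | 5.3 |

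These limits use the stated maximum exposure. They reflect the small exposure and would be the same if numerator and benchmark matched.

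**The case against.** The strongest defence is that the choice is disclosed and reasoned. Research Methods for Specific Aim 1 labels the rate as covering all SAEs and explains that people with DS may have more events without treatment. In a single-arm trial with no DS background rate, counting attributed events is defensible. That stands as a reason for the filter. It does not turn an all-SAE rate into a valid reference for the filtered count.

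Second, the Outcome Measures sentence can be read as stating a necessary condition rather than saying that two or fewer events would suffice. The Specific Aim 1 text weakens that reading, because it defines success of the endpoint as meeting the limit.

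Third, much of the remedy is already planned: study-wide AE rates per 100 PY, the published rates listed for reference, and a yearly check against assumptions. This is correct. A reader might infer that SAEs outside the definite category go unmonitored; the documents do not support that. What is missing is an all-SAE rate with an interval in the primary safety analysis.

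Fourth, a reader might take the wide confidence limits as the measure of the mismatch, or argue that the endpoint fails because no passing count excludes twice the benchmark. Neither follows. The limits describe precision, and the documents state no margin. The answer also changes with the margin and the type of limit: for zero events the one-sided 95% upper limit is 20.7 per 100 PY (2.2 times 9.4), which would exclude a margin of 2.5.

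**Conclusion.** The point holds as a fault in the inference attached to a primary endpoint. The criterion is filtered by attribution and its benchmark is not, so meeting it cannot demonstrate comparability. The comparison is not confined to one sentence: it also appears in hypothesis 1, in Research Methods for Specific Aim 1 and in the Data Analysis Plan.

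The direction is certain, but the size is not known from the documents. The 34% to 99% range rests on assumed attribution shares, an illustrative tripling of the rate and Poisson counts. The low precision is a second, independent reason for caution about any comparability statement.

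The statement that no matched reference rate exists covers only the text available. Part of the Preliminary Studies, the Data and Safety Monitoring Plan named in Section VII and the cited safety source were not seen. A matched rate there could close the gap in hypothesis 1, but would not by itself correct the derivation from the all-SAE rate.

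A reader might also conclude that the stopping rules are wrong. No such finding is made; they share the derivation, and that is all. This should be fixed, but it does not undermine the trial's conduct, since surveillance is intact and only wording and reporting change.

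**What to change.** 1. **Outcome Measures:** delete "in order to demonstrate comparable safety to the typical population".
2. **Research Methods for Specific Aim 1 and the Data Analysis Plan endpoint definition:** keep two as a pre-specified descriptive threshold, and state that meeting it is not evidence of comparability with the published rate.
3. **Hypothesis 1:** restate it as *at most two SAEs rated definitely related to tofacitinib will occur in 16 weeks of treatment*, or keep the comparison and cite a causality-matched reference rate.
4. **Research Methods for Specific Aim 1 and Data Analysis Plan:** replace "a comparable number of SAEs is 1.36" with *the expected number of SAEs of any attribution at this rate is 1.36, which is not a like-for-like reference for definitely related SAEs*. In the Data Analysis Plan, describe the limit as *chosen with reference to* the published data, and restore the note that the rate covers all SAEs.
5. **Data Analysis Plan, Specific Aim 1:** add a descriptive analysis of all SAEs through 16 weeks regardless of attribution, as a count and a rate per 100 actual patient-years with an exact Poisson two-sided 95% CI, shown beside 9.4. Tabulate definitely and possibly related SAEs separately. State that the comparison with rheumatoid arthritis patients is confounded by background morbidity in DS and is imprecise.
6. **Stopping rules 5 and 6:** the sponsor and the DSMB should reconcile these passages with the changes above, since they rest on the same derivation. No rule is proposed here.

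**Cost:** no new data are needed, because every SAE is already recorded, attributed and listed. The price is a weaker safety statement and a visibly wide interval.
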